All patients presenting to Lismore Base Hospital with fractured neck of femur (#NOF) are placed on the NOF pathway. The pathway suggests that patients on the NOF pathway should receive regional anaesthesia (nerve block) within 30 minutes of arriving at the Emergency Department. The nerve block performed will be determined by the treating clinician.

Inclusion and Exclusion Criteria

Inclusion Criteria

1. Adult patients (>18 years) presenting to Lismore Base Hospital Emergency Department with radiologically confirmed #NOF. The neck of femur fractures include:
 - a. Sub-capital fracture
 - b. Surgical neck fracture
 - c. Intertrochanteric fracture
 - d. Peritrochanteric fracture
2. The patient receives a nerve block for their fractured neck of femur in the Lismore Base Hospital Emergency Department
3. The nerve block may occur before or after the radiological confirmation of diagnosis

Exclusion Criteria:

1. Regional anaesthesia not provided in the Lismore Base Hospital Emergency Department
2. Allergy to amide local anaesthetics
3. Infection of the skin overlying at the overlying the site of potential nerve block
4. The patient has already received a nerve block for this fracture prior to arrival in at Lismore Base Hospital
5. Other reason at the discretion of clinician/s
6. Femoral shaft fracture

Block Standardisation

As this is an observational study, intervention is not dictated by the study, but is at the discretion of the treating physician. However, there have been efforts to standardise aspects of the care provided to improve the validity of this observational data.

In accordance with usual standards of practice:

- All nerve blocks are to be performed with ultrasound guidance. Needle tip and infiltration should be directly visualised with ultrasound.
- All nerve blocks are to be performed with continuous cardiac monitoring and intravenous access.

Nerve Block Kit:

To encourage standardisation of nerve blocks within hour department a nerve block kit is already in use. It contains:

- 80 mm x 21 gauge Pajunk SonoSpot needle (or alternative needle stocked by the department)
- 0.9% sodium chloride - 1 x 10mL vial
- 20 mL luer lock syringe
- 3 mL luer lock syringe
- Drawing up needle
- 25 gauge 38 mm or 23 gauge 35mm needle for local infiltration
- Dressing kit
- Chlorhexidine 2% in 70% ethanol skin prep solution (30 mL)
- Sterile ultrasound probe cover and gel

Standard Order Set:

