A standard order set [Appendix 1] has been built into FirstNet (the electronic medical record). This order set includes blood tests, radiography, referrals and analgesia. This “NOF order set” has been approved by the #NOF pathway working group and is available to all medical officers in the Emergency Department. The investigators will facilitate Medical Officers to add this order set to their ‘favourite’ orders.

Data To Be Collected

Regional Anaesthesia Provided

- Type of nerve block
- Content of nerve block
- Experience of practitioner

Patient Demographics

- # NOF Subtype
- Baseline characteristics: age, gender, comorbidities, social history, opioid use

Pain Scores

1. Visual Analogue Scale (VAS) [Appendix 6]
 - a. 100mm scale. Measured in 1mm increments. Converted to a score from zero to ten.
 - c. Measured at rest and on movement
2. Pain Assessment in Advanced Dementia (PAINAD) [Appendix 6]
 - a. Paper or electronic calculator
 - b. Scored zero to ten

Patients who are cognitively intact will have pain scores measured using the VAS, converted to score from zero to ten.

Patients who have a history of significant dementia or who clinically have significant cognitive impairment will have pain scored by a nurse or doctor using the pain assessment in advanced dementia (PAINAD) score, also zero to ten.

Subjective Observed Patient Comfort During Nursing Cares

- A binary measure of analgesia. Adequate or inadequate?

Opioid intake

- At baseline
- Pre-hospital
- In ED prior to regional analgesia
- After regional analgesia

Standard Documentation

Documentation that is recorded as a usual part of patient care

Nerve Block: Clinicians will be encouraged to document the placement of nerve block and its content in a standardised fashion within the patient's medical record, as is usual practice.

Pain Scores: Pain scores are recorded in the electronic medical record alongside vital signs. This is usual practice of nursing staff in the emergency department and on surgical wards. The utilisation of the VAS pain score is however, a departure from usual practice. Other pain scores such as the numerical pain scale and faces pain scale are previously / currently used by nursing staff at Lismore Base Hospital.

Analgesia Intake: Will be recorded in the electronic medical record. This is usual practice.

Additional Documentation

Documentation that is additional to usual practice, for the purpose of this study

Additional Paper Documentation:

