1. SPIED Study Emergency Department Data Form [Appendix 4]
 - a. Emergency Department staff may choose to use this form in place of Medical Surveys should they prefer, or if there are logistical challenges encountered with Medical Surveys
2. Limb Observation Chart: [Appendix 6]
 - a. It is standard practice on the surgical ward for nursing staff to complete limb observations every 1-2 hours on patients with #NOF and record these on a limb observation chart.
 - b. This chart has been modified for the SPIED study to also record pain scores
 - c. Also includes pain score calculators for the VAS and PAINAD
3. Subjective Observed Patient Comfort During Nursing Cares [Appendix 7]

Primary outcome = reduction of pain score

VAS pain scores will be recorded at rest and on movement. Movement is defined as attempted hip flexion to 15 degrees. PAINAD scores will be single measure based on nursing observation.

This score will be documented at the following times:

- Prior to placement of nerve block in the emergency department
- 15, 30, 60 minutes post placement of block
- With routine limb observations on the surgical inpatient ward, approximately hourly

Data will be collected for 12 hours post nerve block (or the next documented score after 12 hours) or until the patient is moved to the operating room, whichever is sooner.

Sample size and statistical power

The rationale for sample size calculations:

- A reduction in visual analogue pain score of 13 mm (1.3/10) was established as being clinically significant by Todd et al in 1996 [26].
- A clinically significant difference between two treatments that reduce pain scores by 1.3/10 has not been well defined
- Cooper et al used 1.5/10 difference in pain scores as a definition of clinically significant difference between blocks [27].
- Newman et al found a standard deviation in pain score reduction of 2.4 in patients receiving regional analgesia for #NOF in 2013 [28]. This figure was used by Cooper et al for their power calculation in 2018.
- Cooper et al found standard deviations of 2.2 and 2.4 respectively for the FNB and FICB [27].
- A retrospective study of patients that received regional anaesthesia for # NOF at LBH in the first 4 months of 2019 was performed by co-investigators of this study. This data included 40 patients that received regional anaesthesia in ED, 6 of whom received a PENG block. Pain score documentation was not sufficiently reliable to inform power calculations for this observational study.

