- ❑ Documentation on a paper form SPIED ED Data Form [Appendix 4] in the emergency department. This is additional to usual documentation and may be replaced by utilising Medical Surveys for data entry in the ED.
- ❑ Subjective Observed Patient Comfort During Nursing Score. May be completed in paper form [Appendix 7] or within Medical Surveys.

Data Governance

Data Storage:

The completed SPIED ED Data Form [Appendix 4] will be filed by clinicians in a folder within the Acute clinical area of the Emergency Department at Lismore Base Hospital. The SPIED ED Data Form will be the enrolment record.. Completed forms will be frequently collected by the investigators and stored securely with the ED Support Offices, which require swipe card access. This data will be stored for 5 years after the completion of data collection and then destroyed.

All other paper forms associated with the SPIED Study will form part of the patient's hospital record and will be treated accordingly.

Data Access:

- Investigators who are clinicians at Lismore Base Hospital have access to the patient's electronic medical records in the usual fashion as they would for day to day clinical work.
 - Investigators who access a patient's file for the purpose of data collection rather than clinical care, will create an electronic entry to document that they are accessing the file for the purposes of the SPIED study.
- In the event that any research funding is obtained, a research assistant may have access to Medical Surveys data and eMR as do the investigators.

Statistical Analysis

Primary Outcome:

Reduction in pain scores over the first 12 hours after nerve block. We will apply the following statistical tests:

- Student's t-test to compare the reduction in pain score of patients who receive a PENGGB compared to FNB and FICB
 - Subgroup analyses of the cognitively impaired and non-cognitively impaired population. These populations will have pain scored by the PAINAD and VAS respectively.
 - Subgroup analysis of FNB and FICB separately

Secondary Outcomes

- Onset of block. Defined as the time until the first pain score ≥ 1.5 less than the pre-block pain score.
 - T-test
- Subjective observed patient comfort during nursing cares
 - Chi Square test
- Patient Preference in the event of crossover
 - Chi Square test
- Rates of block failure. Defined as not achieving a reduction in pain score of $\geq 1.5 / 10$
 - Chi square test

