- Duration of analgesia. End of block effect defined as an increase in pain on movement score to ≤ 1.0 from pre-block pain score for that patient, in a patient who had a reduction in pain score on movement > 1.5 at any time.
 - T-test

Ethical Considerations

There are several ethical considerations in the design and implementation of this study. Throughout the study design process, the authors have consulted with key members of staff within our health service:

- ❑ *Director of Research: [name]*
- ❑ *Orthopaedic Clinical Nurse Specialist: [name]*
- ❑ *Acute Pain Service Clinical Nurse Consultant: [name]*
- ❑ *Surgical Clinical Nurse Educator: [name]*
- ❑ *Geriatric Medicine CMO: [name]*
- ❑ *Department of Anaesthesia Orthopaedic Special Interest Group: [name]*
- ❑ *Department of Anaesthesia research interest group: [name], [name]*
- ❑ *Pain Specialist: [name]*
- ❑ *LBH Nursing Infection Control: [name]*
- ❑ *Rural Research Education Manager: [name]*
- ❑ *Department of Emergency Medicine: Consultant group*
- ❑ *Emergency Department Clinical Nurse Educator: [name]*
- ❑ *Emergency Department Nurse Unit Managers: [name], [name]*
- ❑ *Director of Emergency Medicine Training: [name]*
- ❑ *NOF pathway working group headed by [name]*

Research merit and integrity

Merits of this research:

- We believe the PENGGB to have a superior anatomic basis for efficacy compared to other nerve blocks for neck of femur fractures. Early experience utilising the PENG block is promising.
- Early adoption of the PENGGB which, to our knowledge, has not been studied outside of Toronto, nor within an Emergency Department would place our institution in a leading position in the emergency management of # NOF.
- The generation of evidence supporting this therapy's safety and efficacy would be expected to increase its uptake both within our institution and at other institutions. A positive study would be expected to encourage further investigation in the form of a randomised clinical trial
- Generation of evidence that the PENGGB is inferior to the standard of care would appropriately discourage clinicians from changing their practice.

Integrity:

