This project aims to improve understanding of the PENG block and its effects. We aim to publish results, either positive or negative, in a peer-reviewed journal approved by the Australasiaon College of Emergency Medicine and/or at appropriate scientific meetings.

Justice

All patients presenting to our facility with #NOF will be eligible for inclusion in this study. The patient experience of receiving the PENG block is very similar to that of receiving FNB or FICB and a lay-person would unlikely be able to tell the difference. There is no increased burden on patients enrolled nor on those not enrolled.

Beneficence

We believe that all patients present and future will benefit from the standardisation of practice and the establishment of preferred practice within our health service.

Risk

We do not anticipate that this study exposes participants to an increased risk. As outlined above we believe the PENG block conveys safety advantages compared to standard blocks the FNB and FICB. Most important is the physical separation of the site and the tissue plane of infiltration from major blood vessels. This reduces the risk of local anaesthetic systemic toxicity - which is the most serious adverse event associated with regional anaesthesia. Additionally, the nerves targeted and affected by the PENGGB are small, sensory nerves. Any trauma or toxicity to nerves as a result of a PENGGB would have no effect on motor nerves, which provide power to the thigh. Conversely, both the FICB and FNB effect larger motor nerves and any nerve trauma or toxicity can theoretically affect the muscle power in the thigh. We note that there is poor evidence supporting the argument that regional anaesthesia causes clinically significant trauma or toxicity to motor nerves.

Outcomes and Significance

The PENG block is a new therapy with a sound scientific basis and promising preliminary results both in the limited existing literature and our experience delivering this therapy at Lismore Base Hospital. If it is a superior regional analgesic then it follows that the therapy should be superiorly opioid-sparing. As we know, the study population is particularly at risk of complications from opioid analgesia [5-7]. Also, we know that pain (a result of ineffective analgesia) itself is a risk factor for agitation and delirium [reference] [29-33]. It follows that there would be an improvement in patient safety and patient-important outcomes from wider adoption of a superior intervention.

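### The protocol gives two rules for who scores PAINAD, and one of them lets the clinician who chose and placed the block rate its effect

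*Protocol*

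**What the plan says.** Under Data To Be Collected, Pain Scores, the Protocol assigns the VAS to cognitively intact patients. Patients with significant dementia or cognitive impairment "will have pain scored by a nurse or doctor using the pain assessment in advanced dementia (PAINAD) score, also zero to ten". Nothing limits which doctor this may be.

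The section headed "Primary outcome = reduction of pain score" describes the same measurement differently: "PAINAD scores will be single measure based on nursing observation". It lists a pre-block score in the emergency department (ED), then scores at "15, 30, 60 minutes post placement of block", then scores with routine limb observations on the ward. The Additional Documentation section has nursing staff complete those ward observations.

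The Statistical Analysis section brings PAINAD into the primary outcome. Cognitively impaired and unimpaired patients are named subgroups, and "These populations will have pain scored by the PAINAD and VAS respectively".

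On choice of block, Current Practice says: "The nerve block performed will be determined by the treating clinician". No section bars that clinician from scoring, and none provides a masked or independent rater.

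**The concern.** A VAS score comes from the patient. A PAINAD score is wholly an observer's judgement, so who makes it is part of the definition of the endpoint. Two sections that define the same endpoint differ on this. Under the wider rule, the person who selected and performed the block may judge whether it worked. The rater may also be a doctor at baseline and a nurse later, so that a difference between raters enters the reduction in pain.

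This is a matter of conduct at the bedside. A statistical analysis plan written later cannot recover who rated a patient if the role was not recorded, and cannot undo a rating by the operator. It has to be settled in the protocol.

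**Working it through.** **1. The two rules side by side**

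| Item | Pain Scores section | Primary outcome section |
|---|---|---|
| Measure | PAINAD, 0 to 10 | PAINAD, single measure |
| Who rates | nurse or doctor | nursing observation |
| Block operator excluded? | no | only if the operator is not a nurse |
| Same rater throughout? | not required | not required |

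Both rows on the rater describe the same score, so the sections must be reconciled.

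**2. How the rater enters the outcome**

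Write an observed score as the true score plus a rater error: S(t) = T(t) + r(t), with baseline B = T(0) + r(0). Then

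observed reduction at t = [T(0) − T(t)] + [r(0) − r(t)].

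- Same rater with a constant habit: r(0) = r(t), and the second bracket vanishes.
- Doctor at baseline, nurse later: r(doctor) − r(nurse) remains in every later reduction for that patient, including those from nurse-rated ward scores.
- Operator rates generously after the block: r(t) is negative at the early times and the reduction is inflated there.

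**3. From patient to group comparison**

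Let f be the share of patients on PAINAD, and let D be the mean of r(0) − r(t) among PAINAD patients in an arm. If f is the same in both arms,

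shift in the between-group difference = f × [D(PENG) − D(FNB/FICB)].

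The Protocol gives neither f nor D for either arm. If D is equal in the two arms the shift is zero, and only noise is added. A shift needs D to differ by block type.

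**4. Which scores are exposed**

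Ward scores are made by nurses, so doctor rating mainly concerns the pre-block score and three post-block scores. Assume a patient followed for the full 12 hours, with ward scores from hour 2. Hourly scoring gives 11 ward scores (hours 2 to 12), so 3 of 3 + 11 = 14 post-block scores are exposed, or 21%. Two-hourly scoring gives 6, so 3 of 9, or 33%. In an equally weighted average over 12 hours, post-block operator error would be diluted to about that extent. Error in the baseline would not be diluted, because B enters every reduction.

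**5. Outcomes that turn on one score**

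- Onset (Secondary Outcomes): the first time at which B − S(t) ≥ 1.5.
- Block failure: the maximum over t of B − S(t) is below 1.5.

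A single early reading with S(15 min) ≤ B − 1.5 reclassifies a failure as a success and sets onset at 15 minutes, whatever the later nurse-rated scores show. Ward scoring does not dilute these two outcomes.

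**6. The Protocol's own figure**

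The stated minimum is 74 (25 + 49): one-sided 0.05, power 0.80, SD 2.4, difference 1.5, ratio 1:2. The normal approximation for the smaller arm is (1 + 1/2) × [2.4 × (1.645 + 0.842) / 1.5]² = 23.7, giving 24 + 48 = 72. With the noncentral t distribution, power is 0.797 at 24 + 48 and 0.809 at 25 + 49, which agrees with the stated total. This point does not alter that figure.

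**The case against.** **Nurse scoring is probably the norm.** Standard Documentation says nursing staff in the ED and on surgical wards already record pain scores, and the section that defines the primary outcome names nursing observation. The mention of a doctor may be loose wording. That is fair: the document permits operator scoring but does not say that it will happen, or that the operator is still at the bedside at 15 to 60 minutes. The permission is still written into the rule for the score.

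**A reader might infer a bias towards PENG of a definite size.** For example, assume 20% to 40% of patients on PAINAD and a favourable error of 0.5 to 1.0 point in the PENG arm only. The shift would then be 0.20 × 0.5 = 0.1 to 0.40 × 1.0 = 0.4 point. The document does not support this as a result. The stated belief, "We believe the PENGGB to have a superior anatomic basis for efficacy compared to other nerve blocks for neck of femur fractures", is the authors', whereas the treating clinician chooses the block. The plan expects PENG in only one-third of patients, so most operators will have chosen another block and may favour it equally. With equal error in both arms the shift is 0.40 × (1.0 − 1.0) = 0; with error only in the FNB/FICB arm it is −0.1 to −0.4. The calculation also takes every analysed score as operator-rated, which the nurse-made ward scores contradict.

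**A reader might also infer that the Protocol relies on patients being unable to tell the blocks apart.** The remark that "a lay-person would unlikely be able to tell the difference" stands under Justice and concerns patient experience and burden. It is not offered as masking.

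**The study is openly observational and unmasked, and nurses know the block type too.** This stands as a limit on what the change can achieve. It does not explain why the operator should be allowed to score. Block Standardisation says that aspects of care were standardised to improve the validity of the data, and naming the rater serves the same purpose.

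**Conclusion.** The point holds as an inconsistency with a practical consequence. The Pain Scores and primary outcome sections disagree on who rates PAINAD, and the wider rule allows the clinician who chose and placed the block to rate the baseline and early scores. It also allows the rater type to change between baseline and follow-up.

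The effect is confined to patients scored by PAINAD. There it reaches the primary reduction in pain, mainly through the baseline and the first hour, and it reaches onset and block failure, where one reading can decide the result. A change of rater adds noise; it becomes bias only if it differs by block type. Size and direction cannot be derived from the document, because the PAINAD share, the frequency of doctor scoring and any rater error are all unstated. No numerical shift should be reported as a finding.

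This should be corrected before enrolment because it is avoidable and cheap to avoid. It does not invalidate the design or the sample size.

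**What to change.** - In Data To Be Collected, Pain Scores, delete the alternative of a doctor so that the text agrees with the primary outcome section.
- In both sections, state that PAINAD is scored before and after the block by the bedside nurse, and never by the person who chose or placed the block.
- Ask for the same nurse at the pre-block, 15, 30 and 60 minute scores where possible.
- Record the rater's role with each score, so that any departure can be seen and examined.

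**Cost.** A wording change and, unless the forms already have it, one field on the ED data form and the limb observation chart. Those appendices are not shown, so the field may already exist. No extra assessor is needed, since nurses already record pain scores in both settings. The downside is an occasional missed early score when the nurse is occupied.

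**Limit.** Nurses are not masked to block type, and the rater will still usually change at the move from ED to ward. The change removes rating by the operator and steadies the baseline and first-hour scores; it does not make the scale free of rater bias.

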Minimum Sample Size Calculation: Application of Student's t-Test.

Calculation assisted by using the Simple Sample Size Calculator (Android application). [Appendix 2]

- One-sided test to assess for non-inferiority
- Two sample
- Error 0.05
- Sample allocation ratio of 1:2
- Standard Deviation = 2.4
- $\mu_0 = 4$, $\mu_1 = 2.5$ (difference in pain score reduction of 1.5)
- Target (Actual) Power = 0.8000
- **Sample size = 74 (25+49)**

Duration of Data Collection

At our institution, we had 203 patients present with fractured neck of femur in 2018 and in the first 6 months of 2019 we have had 79. This is an average of 15.67 per month. Presuming this average continues and we achieve an enrolment rate of 80% and a PENG block delivered to one-third of these patients, we could expect to enrol sufficient patients in 6 months. To ensure significant power is achieved, we plan to enrol patients for a minimum of 6 and a maximum of 8 months.

Enrolment may be terminated early if we achieve a minimum enrolment of 125 patients and 41 PENG blocks. These numbers would allow for assessment of superiority (two-sided test) sensitive to a difference in pain score reduction of 1.3/10. [Appendix 3]

Secondary Outcomes

In an attempt to measure patient important outcomes, we will collect data on:

- Onset Time for analgesia (defined as the time until the first pain recorded pain score that is $\geq 1.5 / 10$ less than the pre-block pain score.
- Subjective observed patient comfort during nursing cares
- Patient preference where crossover occurs.
- Rates of block failure
- Block duration of analgesia

Subjective observed patient comfort during nursing cares:

Nursing staff caring for patients will be asked to comment on the patient's pain during standard nursing cares that require movement. These may include:

- Transfer to or from a bed
- Transfer on and off a bedpan
- Change of bedding or pad
- Other

At the time of nursing care, nurses are asked to rate the patient's analgesia as adequate or inadequate

Patient Preference where crossover occurs

- Some patients will have a repeat nerve block in the preoperative phase
- Of this population, some will receive a nerve block that is different to the block they received in ED. Hence they will have received cross over treatment and can act as their own control to compare two blocks.
- Investigators will identify these patients and they will be asked which block they found to provide more comfort.

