- Treatment in this phase of the patient's journey will be decided by the acute pain service or duty anaesthetist. The investigators will have no influence over which repeat block the patient receives.

Block failure

- Defined as maximum pain score improvement of less than 1.5 out of 10.

Duration of analgesia from nerve block

- End of block effect defined as an increase in pain score to ≤ 1.0 from pre-block pain score in a patient who had a reduction in pain score of > 1.5 at any time.

Opioid Requirement

- Opioid intake will be measured by analysis of the electronic medication chart from the insertion of block until 12 hours have passed, or the patient is checked in to the operating theatre, whichever occurs first.
- This information will be converted to milligrams of oral morphine using the Faculty of Pain Medicine Opioid Calculator

Adverse events

In an effort to detect the incidence of adverse events, the investigators will:

- Perform a keyword search of the “Continuous Doc” feature of the electronic record, after the patient is discharged from the hospital.
 - Keywords:
 - Delirium
 - Sedation
 - Constipation / Constipated
 - Aspiration
 - Naloxone
- Review the electronic medication chart for use of:
 - Naloxone
 - Antibiotics

Surgery Waiting Time:

Time to surgery will be defined as the time from Triage in the Emergency Department to the time of Check In at Operating Theatre for operative fixation.

Data collection on our cohort for the purposes of the primary outcome will cease at the time of check in to the operating theatre or at 12 hours after the insertion of nerve block, whichever is sooner.

Mean, median and longest wait times will be recorded. This information will inform future practice at our hospital.

Data Collection and Storage

Primary Data Recording Methods:

Were discussed above and are summarised here:

- ❑ Documentation in the electronic medical record record (PowerChart / FirstNet / SurgiNet) as is usual practice for all patients treated in the emergency department and those admitted to the hospital
- ❑ Documentation on the paper SPIED Limb Observation Chart [Appendix 6] which is usual practice for patients admitted to the inpatient orthopaedic and surgical ward with fractured neck of femur. The standard chart has been modified for the SPIED study to include pain scores and pain score calculators.

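### Crossover preference is called self-controlled and tested by chi-square without regard to order, although the ED block always comes first, so a block can be credited merely for being second

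*Protocol*

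**What the plan says.** Every participant has an ED block. The inclusion criteria require that "The patient receives a nerve block for their fractured neck of femur in the Lismore Base Hospital Emergency Department", and the exclusion criteria remove anyone for whom "The patient has already received a nerve block for this fracture prior to arrival in at Lismore Base Hospital" applies.

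Under Secondary Outcomes, Patient Preference where crossover occurs, the protocol says "Some patients will have a repeat nerve block in the preoperative phase" and "Of this population, some will receive a nerve block that is different to the block they received in ED". It continues: "Hence they will have received cross over treatment and can act as their own control to compare two blocks". The endpoint is a single question: "Investigators will identify these patients and they will be asked which block they found to provide more comfort". Treatment in this phase "will be decided by the acute pain service or duty anaesthetist", and the investigators have no influence on the choice.

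In the Statistical Analysis section, the entry "Patient Preference in the event of crossover" carries a chi-square test and nothing more. The protocol gives no expected number of crossovers, no split between sequences and no table layout for this outcome.

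**The concern.** In a crossover design, patients serve as their own control because the order of treatments is randomised or balanced, so an effect of order does not line up with treatment. Here order lines up with setting. The first block is the ED block, chosen by the treating ED clinician. The second is the preoperative repeat, chosen by another team. Patients enter the comparison only through events after the first block: a repeat was given, and it was of a different type.

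The preference question therefore mixes block type with order and stage of care, and possibly with whatever led to the repeat. Comparing within a patient removes differences between patients. It does not remove differences between the first and second occasion.

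If patients lean towards the later block, and more of them had PENG second than first (or the reverse), that lean shows up as a preference for a block type. The protocol presents this among outcomes meant to capture what matters to patients, so a significant result would carry weight with readers.

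**Working it through.** **Plan's own figure.** None exists for this outcome, so there is nothing to reproduce.

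**Step 1: is order fixed?** Yes. The inclusion criterion requires an ED block, and the exclusion criterion rules out an earlier block for the same fracture. The ED block is first for everyone, and any repeat is second.

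**Step 2: is order balanced across block types?** Nothing secures it. Under Duration of Data Collection, the protocol expects PENG in one-third of patients. If crossovers followed that mix, and every repeat after a non-PENG block were PENG, two-thirds would have PENG second. That is an illustration; the second block is the clinician's choice.

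**Step 3: what does a 50:50 chi-square do when the blocks are equal?** All inputs here are assumptions:
- a patients have PENG second, b have PENG first, and n = a + b;
- q is the probability of preferring whichever block came second.

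The number preferring PENG, k, is Binomial(a, q) + Binomial(b, 1 − q), with mean a·q + b·(1 − q). The test rejects when (2k − n)²/n > 3.841. That means k ≥ 10 or ≤ 2 for n = 12, k ≥ 15 or ≤ 5 for n = 20, and k ≥ 21 or ≤ 9 for n = 30.

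Example: a = 20, b = 10, q = 0.7 gives 20 × 0.7 + 10 × 0.3 = 17 of 30 expected to prefer PENG (56.7%). At q = 0.8 it is 16 + 2 = 18 of 30 (60%), although the blocks are equal.

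Exact rejection probabilities:

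| PENG second + PENG first | q = 0.5 | q = 0.7 | q = 0.8 |
|---|---|---|---|
| 15 + 15 | 4.3% | 2.7% | 1.2% |
| 8 + 4 | 3.9% | 4.2% | 4.0% |
| 13 + 7 | 4.1% | 5.3% | 6.0% |
| 20 + 10 | 4.3% | 8.1% | 12.4% |
| 24 + 6 | 4.3% | 22.7% | 49.3% |
| 12 + 0 | 3.9% | 25.3% | 55.8% |
| 20 + 0 | 4.1% | 41.6% | 80.4% |

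In the 20 + 10 row nearly all rejections favour PENG. Reversing the split to 10 + 20 gives the same rates against PENG.

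**Step 4: does analysis by sequence help?** Let d be the shift in preference towards PENG. The proportion preferring the second block is then q + d when PENG is second and q − d when PENG is first. The difference is 2d, so q cancels, and with equal blocks the expected difference is zero. With 20 + 10 patients, a chi-square of sequence by preferred position rejects in 5.2%, 5.0%, 4.7% and 3.7% at q = 0.5, 0.6, 0.7 and 0.8. Fisher's exact test on the same table, by full enumeration, stays between 2.2% and 3.1%. A common order effect no longer inflates the error.

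**Step 5: what remains?** The step 4 comparison assumes the same q in both sequences. If repeat blocks are given for different reasons after PENG than after other blocks, or the choice of second block depends on how the first performed, q differs between sequences and some bias stays.

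**The case against.** The strongest reply is that the harm depends on quantities the protocol does not give. With balanced sequences there is no inflation. With two-thirds PENG-second and only 12 or 20 crossovers, the rate is 4.0-6.0%, close to nominal. The chi-square entry does not name a table, and a sequence-by-preferred-position table would fit the wording and remove a common order effect. Table layout may be left to an analysis plan that is not shown. The study is openly observational, this is one secondary outcome, and no sample size or primary conclusion depends on it.

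That limits size and severity. It does not rescue the statement that the patients act as their own control, which is a stated premise that the design contradicts and that a later analysis plan would have to reverse.

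A reader might infer more than the documents support:
- **Error rates of 25-80% are to be expected.** They need every crossover to be in one sequence, which nothing in the protocol says.
- **The test counts each patient twice.** No such table is specified.
- **FNB-FICB crossovers are pooled into the PENG comparison.** The protocol says only that two blocks are compared.
- **Repeat blocks follow failed or worn-off first blocks, given by a different operator.** This is plausible, but no reason for repeating is stated, and the text says who decides on the block, not who performs it.

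**Conclusion.** The point holds as a minor one. The self-control claim is unsupported: order is fixed by setting, the second block is chosen by clinicians, and entry depends on being re-blocked with a different type. An analysis that ignores order can credit a block for coming second.

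The size and direction of the effect in this study are unknown. The figures above rest on equal blocks, an assumed 70-80% preference for the second block, and assumed numbers and splits of crossovers. Under those assumptions the false-positive rate runs from no inflation (balanced), through about 8-12% (20 PENG-second, 10 PENG-first), to 25-80% with 12-20 patients in the one-sequence extreme. The primary outcome is not affected.

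**What to change.** - Delete the statement that these patients can act as their own control.
- Tabulate preference by sequence: PENG then other, and other then PENG.
- If a test is wanted, compare the proportion preferring the second block between the two sequences with Fisher's exact test.
- If only one sequence occurs, report counts without a test.
- Label the result exploratory, because selection for re-blocking and the non-random choice of second block remain after the order effect is removed. Reporting the reason for and timing of each repeat block, where recorded, would help readers judge this.

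The change is to analysis wording only and needs no new patients. Its cost is that, with few crossovers, the outcome becomes descriptive.
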